6.2 SAFETY MEASURES

- Incidence and severity of ocular AEs
- Incidence and severity of non-ocular AEs
- BCVA at all visits
- Slit-lamp biomicroscopy at all visits
- Drop comfort assessment (Visits 2)
- Intraocular pressure (Visits 1 and 6)
- Dilated fundoscopy (Visits 1 and 6)
- Immunogenicity to HL036 in Serum (Visits 2, 4, 5, and 6)

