9.2 SERIOUS ADVERSE EVENTS

An AE is considered serious if, in the view of either the investigator or sponsor, it results in any of the following outcomes:

- Death;
- A life-threatening AE;

Note: An AE is considered "life-threatening" if, in the view of either the investigator or sponsor, its occurrence places the subject at immediate risk of death. It does not include an AE that, had it occurred in a more severe form, might have caused death.

- Inpatient hospitalization or prolongation of existing hospitalization;

Note: The term "inpatient hospitalization" refers to any inpatient admission (even if less than 24 hours). For chronic or long-term inpatients, inpatient admission includes transfer within the hospital to an acute/intensive care inpatient unit. Inpatient hospitalization does not include: emergency room visits; outpatient/same-day/ambulatory procedures; observation/short stay units; rehabilitation facilities; hospice facilities; nursing homes; or clinical research/phase 1 units.

Note: The term "prolongation of existing hospitalization" refers to any extension of an inpatient hospitalization beyond the stay anticipated or required for the reason for the initial admission as determined by the investigator or treating physician.

- A persistent or significant incapacity or substantial disruption of the ability to conduct normal life functions;

Note: A serious adverse event (SAE) specifically related to visual threat would be interpreted as any potential impairment or damage to the subject's eyes (eg, hemorrhage, retinal detachment, central corneal ulcer or damage to the optic nerve).

- A congenital anomaly/birth defect.

Important medical events that may not result in death, are life-threatening, or require hospitalization may be considered serious when, based upon appropriate medical judgment, they may jeopardize the subject and may require medical or surgical intervention to prevent one of the outcomes listed in this definition.

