A maximum effort should be made to identify each letter on the chart. When the subject says he or she cannot read a letter, he or she should be encouraged to guess. If the subject identifies a letter as 1 of 2 letters, he or she should be asked to choose 1 letter and, if necessary, to guess. When it becomes evident that no further meaningful readings can be made, despite encouragement to read or guess, the examiner should stop the test for that eye. However, all letters on the last line should be attempted as letter difficulties vary and the last may be the only one read correctly. The number of letters missed or read incorrectly should be noted.

LogMAR Visual Acuity Calculations

The last line in which a letter is read correctly will be taken as the base logMAR reading. To this value will be added the number "N x 0.02" where 'N' represents the total number of letters missed up to and included in the last line read. This total sum represents the logMAR VA for that eye.

For Example: Subject correctly reads 4 of 5 letters on the 0.2 line, and 2 of 5 letters on the 0.1 line.

Base logMAR	= 0.1
N (total number of letters incorrect on line 0.2 as well as 0.1)	= 4
N x T (T=0.02)	= 0.08
Base logMAR + (N x T)	= 0.1 + 0.08
logMAR VA	= 0.18

Repeat the procedure for the left eye.

In order to provide standardized and well-controlled assessments of VA during the study, all VA assessments at a single site must be consistently done using the same lighting conditions and same correction if possible during the entire study. If the same correction cannot be used (ie, a subject forgets his glasses), the reason for the change in correction should be documented.

Slit Lamp Biomicroscopy Procedures

Slit lamp biomicroscopic observations will be graded as Normal or Abnormal. Abnormal findings will be categorized as clinically significant (findings that may interfere with study parameters or otherwise confound the data as determined by the investigator) or not clinically significant (NCS). The following will be examined:

- Cornea
- Conjunctiva
- Anterior Chamber
- Iris
- Lens
- Eyelid

External magnification and biomicroscopy will be performed using a slit-lamp. Magnification will be consistent with standard clinical practice. The subject will be seated.

Dilated Fundoscopy

Dilated fundoscopy will be performed using indirect ophthalmoscopy. The investigator will make observations of the vitreous, retina, macula, choroid and optic nerve.

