Observations will be graded as Normal or Abnormal. Abnormal findings that are clinically significant (as determined by the investigator that may interfere with study parameters or otherwise confound the data) and those that are not clinically significant will be described. A dilated fundoscopy examination should be performed if retinal disease is detected.

- Vitreous: Examination should emphasize the visual axis.
- Retina, Macula, Choroid: Include an observation of the retina and its blood vessels. Eyes should be excluded from the study if active inflammation is present.
- Optic Nerve: Significant damage or cupping to the optic nerve should be noted.

It is recommended that tropicamide 1% ophthalmic solution be used to dilate subjects. The use of cyclopentolate 1% ophthalmic solution is recommended as secondary dilating medication, should the need arise.

Intraocular Pressure

Intraocular pressure (IOP) will be measured in each eye by contact tonometry by the examiner and the results will be recorded in mmHg. A single measurement is made to obtain a determination of IOP. The same tonometer employing the Investigator's standard technique will be used throughout the study. In addition, all reasonable efforts will be made to have the same examiner obtain all IOP measurements for a given subject.

Tear Collection

Subjects will be seated at a reclined position. The investigator will collect tears for up to 5 min from each eye. The right eye will be collected, followed by the left eye. Once tears are collected, they will be pipetted into a separate tube for storage. Further details on tear collection process and storage will be found in a separate manual.

Blood Sampling for Immunogenicity Testing

Serum blood draws will be collected at Visits 2, 4, 5 and 6 for immunogenicity testing. Instructions for the collection, handling and shipping blood for immunogenicity testing are given in a separate laboratory manual.

Ora proprietary scales – Not for distribution without permission

Ora Calibra® Ocular Discomfort Scale for Dry Eye

Ora Calibra® Ocular Discomfort & 4-Symptom Questionnaire for Dry Eye

Visual Analogue Scale (VAS)

Subjects will be asked the following questions regarding ocular discomfort (unrelated to study drug instillation) at all visits.

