### **15.3 Slit-Lamp Biomicroscopy Examination**

A slit-lamp biomicroscopy examination of the cornea, conjunctiva, anterior chamber, iris, lens, and lid will be performed at each visit, and potentially at an Early Termination Visit. Both pre- and post-CAE® examinations will be made at Visits 1, 2, 4, 5, and 6. The results will be graded as normal, Abnormal Not Clinically Significant (NCS) or Abnormal Clinically Significant (CS). Abnormal findings will be described.

The results will be summarized using counts and percentages for each treatment group at each visit for each eye (study eye and fellow eye). Percentages will be based on the number of subjects in each treatment group with responses. Shift tables for the slit-lamp biomicroscopy parameters will also be provided comparing each follow-up visit to baseline. A subject listing of the slit-lamp biomicroscopy parameters will also be produced.

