### **15.4 Dilated Fundoscopy Examination**

A dilated fundoscopy exam will be performed during the study post-CAE® at Visits 1 and 6, and potentially at an Early Termination Visit. Observations will be graded as Normal or Abnormal NCS or Abnormal CS. Abnormal findings will be described. The following will be examined:

- Vitreous
- Retina
- Macula
- Choroid
- Optic Nerve

The results will be summarized using counts and percentages for each treatment group at each visit for each eye (study eye and fellow eye). Percentages will be based on the number of subjects in each treatment group with responses. Shift tables for the undilated fundoscopy parameters will also be provided comparing Visit 6 to baseline (Visit 1). A subject listing of the undilated fundoscopy parameters will also be produced.

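### The NCS/CS grade in the slit-lamp and fundus safety tables is defined by interference with the data, so it does not reliably measure harm to the eye

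*Protocol*

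**What the plan says.** Protocol Appendix 2 (Slit Lamp Biomicroscopy Procedures) grades each structure Normal or Abnormal and then splits the abnormal ones: "Abnormal findings will be categorized as clinically significant (findings that may interfere with study parameters or otherwise confound the data", in the investigator's judgement. Everything else abnormal is NCS. The Dilated Fundoscopy text of the same appendix uses the same test: "Abnormal findings that are clinically significant (as determined by the investigator that may interfere with study parameters or otherwise confound the data".

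Both examinations are safety measures. Protocol 6.2 lists "Slit-lamp biomicroscopy at all visits", with fundoscopy at Visits 1 and 6.

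The SAP uses the grades as reporting categories. For the slit lamp (15.3): "The results will be graded as normal, Abnormal Not Clinically Significant (NCS) or Abnormal Clinically Significant (CS". For the fundus (15.4): "Observations will be graded as Normal or Abnormal NCS or Abnormal CS". Counts and percentages are given by arm, visit and eye. SAP 15.3 adds: "Shift tables for the slit-lamp biomicroscopy parameters will also be provided comparing each follow-up visit to baseline". SAP 15.4 does the same for Visit 6 against Visit 1. Neither section says what makes a finding CS, so the protocol wording governs.

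**The concern.** The test asks whether a finding disturbs the study's data. It does not ask whether the finding matters to the eye. That suits a screening examination, where the question is whether the subject should enter. It does not suit an on-treatment safety grade, where a reader of the table takes CS to mean medically important.

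The NCS/CS split is the only grading of abnormal findings in Tables 14.3.3.1, 14.3.3.2, 14.3.4.1 and 14.3.4.2. If it tracks data quality instead of harm, the CS counts in each arm cannot be read as a safety result. Here those tables carry some weight: the only earlier clinical exposure described (Protocol 1.2) is two instillations in one day in healthy male volunteers, whereas this trial doses patients for eight weeks.

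**Working it through.** The point is definitional and there is no figure in the plan to reproduce. The check sets the relevant texts side by side.

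1. **How each section decides that an ocular finding matters.**
   - Exclusion 1 (Protocol 5.4), for entry: the condition needs treatment, and/or the investigator thinks it may interfere with study parameters.
   - Appendix 2, for grading: interference with study parameters or confounding of the data, as the investigator judges. The need-for-treatment limb is absent, so the safety grade is narrower on this side than the entry criterion.
   - Protocol 9, for AEs: any deterioration in a finding that is clinically relevant.
   - Protocol 9.2, for SAEs: potential damage to the eyes, with the examples "eg, hemorrhage, retinal detachment, central corneal ulcer or damage to the optic nerve".

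   Only Appendix 2 makes no reference to treatment, clinical relevance or damage.

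2. **Signs that the wording was written for screening.** Protocol 8.3.1 gives exclusion of disallowed ocular conditions as the reason for the Visit 1 slit lamp. The fundus text in Appendix 2 itself contains an instruction to exclude eyes with active inflammation. Nothing there separates entry grading from on-treatment grading.

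3. **What the study parameters are.** Appendix 2 does not define them. Protocol Section 6 carries that title and covers both efficacy (6.1) and safety (6.2), including BCVA and IOP. OSDI and the VAS are secondary endpoints and ask about vision and photophobia. A finding that lowers acuity or causes symptoms can therefore be CS under the stated rule. What can fall through is a finding that spares vision, symptoms, ocular-surface measures and pressure.

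4. **Two such findings, followed through the outputs.**
   - A new vision-sparing peripheral retinal lesion at Visit 6. Appendix 2 permits NCS. It appears as Abnormal NCS in Table 14.3.4.1, as Normal to NCS in Table 14.3.4.2 if the retina was Normal at Visit 1, and with its description in Listing 16.2.8.3. If clinically relevant it is also an AE, and if it falls under the visual-threat note it is an SAE. The same eye can then carry an SAE and an NCS grade.
   - A medically important finding confined to the fellow eye. Both primary endpoints are study-eye measures (Protocol 6.1.1, 10.4.2; SAP 9.1), while safety covers both eyes. If it does not lower acuity or change subject-level symptom scores, the rule again points towards NCS.

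5. **Timing of the fundus examination.** The only scheduled post-baseline fundus examination is at Visit 6. Protocol 8.3.6 lists it after every sign and symptom assessment, and 8.3 requires the listed order. No efficacy measurement remains to be disturbed; the investigator can only ask whether those already taken were affected.

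6. **The ordering behind a shift table.** Protocol 10.4.7 also plans shifts from baseline to the worst on-treatment value for ocular safety assessments. Ranking CS as worse than NCS makes sense only if CS means worse for the eye. Under the present definition, a structure that is NCS at baseline and deteriorates without disturbing study measurements can stay NCS and show no shift.

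**The case against.** The strongest reply is that this is clumsy wording with little consequence. Study parameters, read with Section 6, include acuity, and OSDI and the VAS pick up visual symptoms. The rule has a second limb, confounding of the data, which an investigator could apply to a finding whose treatment would bring in a prohibited topical medication or lead to withdrawal. The decision is left to judgement and is not mechanical. Ocular TEAEs are tabulated by arm, by eye and by maximal severity. Abnormal findings are described whether NCS or CS, and optic-nerve damage is to be noted. The Normal/Abnormal division does not depend on the disputed wording.

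All of that stands, and it sets the limits of the point. It rules out three stronger conclusions that a reader might draw:

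- That a retinal detachment, optic-nerve change or lens opacity must be graded NCS, or that almost no posterior finding could be CS. The documents do not support this: a finding that affects vision can meet the rule through BCVA, OSDI, the VAS or the confounding limb.
- That the planned safety tables would be wrong. Only the CS/NCS split is unreliable; the count of abnormal findings is not affected.
- That the number of gradings made measures the damage. Per completer there are (1 + 2 + 2 + 2) × 6 structures × 2 eyes = 84 post-baseline slit-lamp gradings and 5 × 2 = 10 fundus gradings. For 3 × 45 = 135 expected completers that is 84 × 135 = 11,340 and 10 × 135 = 1,350. These are all scheduled gradings, including Normal ones, to which the CS test never applies.

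The reply does not remove the core of the point. On any reading, the grade turns on interference with the data and not on harm, and leaving that to judgement without a medical criterion invites differences between sites.

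**Conclusion.** The point holds in a limited form. A stated rule, not a missing detail, allows a medically important finding to be labelled NCS in on-treatment safety tables, and nothing in the SAP corrects it. The CS/NCS split should not be read as a measure of ocular harm while the definition stands.

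The finding would be misgraded, not lost. It remains in the Abnormal count, shows as a shift from Normal to Abnormal where the structure was Normal at baseline, and should be captured under the AE and SAE rules. Alpha, power and both primary endpoints are unaffected. The documents give no rate of abnormal findings, nor of findings that are important yet do not interfere, so the number of misgraded findings cannot be estimated.

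This rests on two assumptions: that the Appendix 2 definition governs the SAP categories because the SAP offers none, and that investigators apply it as written. Any eCRF completion guidance that defines CS differently is not among the documents.

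**What to change.** - In Appendix 2, define CS for post-randomization slit-lamp and fundus examinations as an abnormal finding that the investigator judges medically important to the eye or the subject, whether or not it affects any study measurement.
- Keep the interference wording for eligibility at Visits 1 and 2, or record it as a separate yes/no flag. The baseline examinations (usually Visit 2 for the slit lamp, Visit 1 for the fundus) also need the medical-importance grade, so that the shift tables compare like with like. A separate flag is the simplest way to do both.
- Reconcile the two Appendix 2 definitions with Exclusion 1, Protocol 9 and Protocol 9.2, and repeat the definition in SAP 15.3 and 15.4.
- No new rule for entering findings as AEs is needed; Protocol 9 already requires clinically relevant deterioration to be recorded.

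The cost is a few sentences in the protocol and SAP, a line of eCRF guidance and, if used, one extra flag. There is no new examination. The downside is that some findings may be graded CS that would not be under the current wording.

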**List of Abbreviations**

ADA	Anti-drug Antibodies
AE	Adverse Event
ANCOVA	Analysis of Covariance
ATC	Anatomical Therapeutic Chemical Classification
BCVA	Best Corrected Visual Acuity
CAE	Controlled Adverse Environment
CI	Confidence Interval
CRF	Case Report Form
CRO	Contract Research Organization
CS	Clinically Significant
CSR	Clinical Study Report
DMP	Data Management Plan
eCRF	Electronic Case Report Form
ETDRS	Early Treatment of Diabetic Retinopathy Study
HIPAA	Health Information Portability and Accountability Act
ICH	International Conference on Harmonisation
IOP	Intraocular Pressure
IP	Investigational Product
ITT	Intent-to-Treat
LOCF	Last Observation Carried Forward
logMAR	Logarithm of the Minimum Angle of Resolution
MCMC	Markov Chain Monte Carlo
MedDRA	Medical Dictionary for Regulatory Activities
NCS	Not clinically significant
OSDI	Ocular Surface Disease Index
PDF	Portable Document Format
PP	Per Protocol
PT	Preferred Term
RTF	Rich Text Format
SAAS	Software-as-a-Service
SAE	Serious Adverse Event
SAP	Statistical Analysis Plan
SD	Standard Deviation
SDC	Statistics and Data Corporation, Incorporated
SOC	System Organ Class
SOP	Standard Operating Procedure
TEAE	Treatment-Emergent Adverse Event
TE-SAE	Serious Treatment-Emergent Adverse Event
TFBUT	Tear Film Break-Up Time
VA	Visual Acuity

VAS	Visual Analogue Scale
WHO DDE	World Health Organization Drug Dictionary Enhanced

## 1. Introduction

The purpose of this statistical analysis plan (SAP) is to describe the planned analyses and reporting for protocol HL036-DED-US-P201 Amendment 1, dated 31OCT2017.

This SAP is being written with due consideration of the recommendations outlined in the most recent International Conference on Harmonization (ICH) E9 Guideline entitled Guidance for Industry: Statistical Principles for Clinical Trials and the most recent ICH E3 Guideline, entitled Guidance for Industry: Structure and Content of Clinical Study Reports (CSR).

This SAP describes the data that will be analyzed and the subject characteristics, efficacy, and safety assessments that will be evaluated. This SAP provides details of the specific statistical methods that will be used. The statistical analysis methods presented in this document will supersede the statistical analysis methods described in the clinical protocol. If additional analyses are required to supplement the planned analyses described in this SAP they may be completed and will be identified in the CSR.

## 2. Study Objectives

The objective of this study is to compare the safety and efficacy of 0.10% and 0.25% HL036 Ophthalmic Solutions to placebo for the treatment of the signs and symptoms of dry eye.

## 3. Study Variables

### 3.1 Primary Efficacy Endpoints

The primary efficacy endpoints are:

- Change from baseline in pre-Controlled Adverse Environment® (CAE®) inferior corneal staining score in the designated study eye as assessed by the Ora Calibra® Corneal and Conjunctival Staining Scale for Grading of Fluorescein Staining at Visit 6 (Day 57, Week 8)

and

- Change from baseline in pre-CAE® ocular discomfort in the designated study eye as assessed by the Ora Calibra® Ocular Discomfort Scale at Visit 6 (Day 57, Week 8)

### 3.2 Secondary Efficacy Endpoints

- Fluorescein staining by region: central, superior, inferior, temporal, nasal and corneal sum as assessed by the Ora Calibra® Corneal and Conjunctival Staining Scale for Grading of Fluorescein Staining at all time points

- Lissamine green staining by region: central, superior, inferior, temporal, nasal, and conjunctival sum as assessed by the Ora Calibra® Corneal and Conjunctival Staining Scale for Grading of Lissamine Staining at all time points
- TFBUT® at all timepoints assessed
- Conjunctival redness as assessed by the Ora Calibra® Conjunctival Redness Scale for Dry Eye at all timepoints assessed
- Schirmer's Test (unanesthetized) at all timepoints assessed
- Symptoms as assessed by the Ora Calibra® Ocular Discomfort Scale and Ora Calibra® Ocular Discomfort and 4-Symptom Questionnaire at all timepoints
- Visual Analog Scale (VAS) Ocular Discomfort at all timepoints assessed
- OSDI® at all timepoints assessed
- Drop comfort as assessed by the Ora Calibra® Drop Comfort Scale, and the Ora Calibra® Drop Comfort Questionnaire at all timepoints assessed
- Daily diary
- Tear mediators

Change from baseline and change from pre- to post-CAE® will also be assessed where appropriate.

### 3.3 Safety Variables

The safety variables include the following:

- Incidence and severity of ocular Adverse Events (AE)
- Incidence and severity of non-ocular AEs
- Best-Corrected Visual Acuity (BCVA) at all visits
- Slit-lamp biomicroscopy at all visits
- Drop comfort assessment (Visit 2)
- Intraocular pressure (IOP) (Visits 1 and 6)
- Dilated fundoscopy (Visits 1 and 6)
- Immunogenicity to HL036 in Serum (Visits 2, 4, 5, and 6)

### 3.4 Statistical Hypotheses

The statistical hypotheses are stated in terms of one-sided hypotheses, although statistical testing will be two-sided.

$H_{01}$ : There is no difference between HL036 ophthalmic solution (0.25% or 0.10%) and placebo in the change from baseline of the pre-CAE® inferior corneal fluorescein staining at Visit 6 (Day 57 ± 3), using the Ora Calibra® scale.

$H_{11}$ : The change from baseline of the pre-CAE® inferior corneal fluorescein staining at Visit 6 (Day 57 ± 3) using the Ora Calibra® scale is less with HL036 ophthalmic solution (0.25% or 0.10%) than with placebo.

$H_{02}$ : There is no difference between HL036 ophthalmic solution (0.25% or 0.10%) and placebo in the change from baseline of the pre-CAE® ocular discomfort evaluated at Visit 6 (Day 57 ± 3), using the Ora Calibra® Ocular Discomfort Scale.

$H_{12}$ : The change from baseline of the pre-CAE® ocular discomfort at Visit 6 (Day 57 ± 3) using the Ora Calibra® Ocular Discomfort Scale is less with HL036 ophthalmic solution (0.25% or 0.10%) than with placebo.

